Mifepristone as an Adjunct to Transcervical Balloon for Labor Induction (MiLI): A Randomized Clinical Trial National Clinical Trial (NCT) Identified Number: 05097326 Principal Investigators: [name], MD and [name], MD MS Research Coordinator: [name], Medicine

May 11, 2022

Mifepristone as an Adjunct to Transcervical Balloon for Labor Induction: A Randomized Clinical Trial (MiLI)

Objective: Our goal is to generate preliminary data on perinatal outcomes, establish recruitment feasibility, and medication tolerability among patients who receive mifepristone for labor induction for live birth. Our aims are to 1) generate preliminary data on the impact of mifepristone use on obstetric and neonatal outcomes and 2) examine recruitment feasibility and willingness of participants to be randomized to guide recruitment periods for future studies

Organization: Stanford University School of Medicine, Department of Obstetrics and Gynecology

Clinical Center: Stanford/LPCH OB clinic and Labor & Delivery

Design Type: Parallel group, two-arm, non-blinded, randomized control trial

Inclusion Criteria:

- 1. Pregnant patients between ages 18 to 45 years
- 2. Singleton, live gestation
- 3. Nulliparous
- 4. Gestational age between 37 weeks 0 days 42 weeks 0 days
- 5. Fetus in cephalic presentation
- 6. Patients admitted for labor induction
- 7. Patients who are not in labor with intact membranes

8 Patients with no contraindication for vaginal delivery (placenta previa, vasa previa, active genital herpes)

9. Patients with no contraindications for mifepristone (chronic adrenal failure, concurrent longterm corticosteroid therapy, history of allergy to mifepristone, or other prostaglandins, hemorrhagic disorders or concurrent anticoagulant therapy, inherited porphyria, or an intrauterine device (IUD) in place)

10. Patients with a Bishop score <6 at time of randomization

11. Transcervical balloon in place <3 hours prior to the time of randomization without prior cervical preparation

*For patients who meet the above inclusion criteria 1-10 and who those who decline randomization will be offered enrollment for chart review only.

Exclusion Criteria:

1. Significant cardiac, renal, or hepatic maternal comorbidities, severe gestational hypertension or preeclampsia with severe features

- 2. Pregnancies complicated by major fetal anomalies
- 3. Patients with a uterine scar
- 4. Pregnancies complicated by fetal growth restriction (Estimated fetal weight <10%)

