 - b. Review of electronic medical record will include pregnancy dating information using the initial ultrasound, and medical history information taken at the prenatal visits or time of admission. Baseline information, including contact information, vitals, demographics, pregnancy history information, and maternal and neonatal medical information will be reviewed to assess eligibility for study participation.
 - c. Patients will undergo a fetal non-stress test at time of admission as part of standard of care. The OB provider or PI's will review the non-stress test. Category 1 or not a persistently Category 2 or 3 fetal heart tracing, according to ACOG criteria is required for eligibility.
 - d. Patients will undergo a cervical exam by the OB provider at time of admission as part of standard of care, to assess for eligibility.
- III. Patients screened at LPCH OB clinic will be screened by chart review
 - a. Patients will need to be scheduled for a term labor induction at LPCH
 - b. Review of electronic medical record will include pregnancy dating information using the initial ultrasound, and medical history information taken at the prenatal visits or time of admission. Baseline information, including contact information, vitals, demographics, pregnancy history information, and maternal and neonatal medical information will be reviewed to assess eligibility for study participation.

Throughout screening period we will record number of patients screened, eligible, and approached in the REDCap database.

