12.2 Sample size determination

We plan to recruit 15 patients per group (30 total) based on the "rule of 12" that is recommended for pilot studies that aim to estimate average values and variability to plan larger studies,²⁴ and to accommodate an estimated 25% intrapartum cesarean rate. Based on 80% power, a two-sided alpha of 0.05, and prior data, we estimate that this sample size would enable us to detect a difference of at least 25 uterine contractions between the two study groups (140-150 on average during labor for patients induced with misoprostol and Cook balloon).

There were approximately 800 inductions among nulliparous patients at LPCH in 2020. We anticipate excluding ~200 patients based on eligibility criteria. Based on previous institutional studies and institutional practices, we expect 50% of patients to be approached for enrollment based on our experience and approximately 50% of patients who are approached to agree to participate in research study. This will result in approximately 150 patients who would agree to participate during one year.

The analysis plan and sample size calculation were developed in consultation with Maternal-Fetal Medicine Senior Biostatistician, [name] (Co-I).

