12.3 Analyses

We will compare the number of uterine contractions and other continuous variables using Mann-Whitney U test and will use Fisher's exact test for categorical variables. Differences will be considered statistically significant using two-sided tests (P<0.05).

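### Section 12.3 plans only unadjusted tests and promises no effect estimate, confidence interval or SD, although the pilot is sized to estimate averages and variability and Bishop score is known before randomization

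*Combined protocol and SAP*

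**What the plan says.** Section 12.3 is the whole analysis section. It states "We will compare the number of uterine contractions and other continuous variables using Mann-Whitney U test" and "will use Fisher's exact test for categorical variables", both two-sided at 0.05. The synopsis adds that analysis is by intention to treat. No covariate, regression, effect estimate, confidence interval or SD is mentioned.

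Sections 4.4 and 12.2 set 15 women per group by a pilot-study rule whose declared aim is to learn averages and variability for planning larger trials. Section 12.2 adds a power statement, "Based on 80% power, a two-sided alpha of 0.05, and prior data", under which the design can "detect a difference of at least 25 uterine contractions between the two study groups", against a reference level of "140-150 on average during labor for patients induced with misoprostol and Cook balloon". It does not state the SD behind this.

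Two baseline quantities are checked before allocation:

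- **Bishop score.** Inclusion criterion 10 requires a score below 6. Section 5.1 says "Patients will undergo a cervical exam by the OB provider at time of admission as part of standard of care", Section 6 has the cervical exam reviewed before randomization, and Section 6.2 says that exams are recorded.
- **Balloon time.** Inclusion criterion 11 reads "Transcervical balloon in place <3 hours prior to the time of randomization".

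Section 6 describes 1:1 blocks and no stratification.

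**The concern.** A pilot meant to supply means and variability should say which estimates it will report. As Section 12.3 stands, its output is a set of p-values. A later trial needs a difference with its interval and an SD with its uncertainty. If that trial will adjust for baseline, it also needs the residual SD.

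Bishop score is the protocol's own measure of cervical readiness, is known before allocation, and is used in neither design nor analysis. If it predicts the outcome, an adjusted estimate would be more precise and would remove the effect of chance imbalance. With 15 per arm, a difference in baseline means above 0.5 SD is not rare: 0.5/√(2/15) = 1.37, a two-sided probability of about 17%.

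If the covariate is chosen only after the data are seen, the choice is open to selection.

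**Working it through.** **The plan's own figure.** With no SD stated, the power claim can only be solved backwards. For n = 15 per group, difference 25, two-sided 0.05 and 80% power:

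SD = 25 / [(1.960 + 0.842) × √(2/15)] = 25 / 1.023 = 24.4 contractions.

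The t-test version gives 23.6. Neither value can be checked against the documents.

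**Effect of adjustment.** With N = 30, k covariates and a share R² of outcome variance explained, the variance of the adjusted difference relative to the unadjusted one is about

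ratio = (1 − R²) × (1 + k/(N − k − 3)).

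The second factor is the price of estimating the covariate effects. It is 1 + 1/26 = 1.038 for k = 1 and 1 + 2/25 = 1.08 for k = 2. Equivalent sample size is 30/ratio, and detectable difference is 25 × √ratio. R² is an assumption, since the documents give none.

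| Assumed R² | One covariate: ratio | Equivalent n | Detectable | Two covariates: ratio | Equivalent n | Detectable | Power, two covariates |
|---|---|---|---|---|---|---|---|
| 0 | 1.04 | 29 | 25.5 | 1.08 | 28 | 26.0 | 76.7% |
| 10% | 0.93 | 32 | 24.2 | 0.97 | 31 | 24.6 | 80.9% |
| 20% | 0.83 | 36 | 22.8 | 0.86 | 35 | 23.2 | 85.2% |
| 30% | 0.73 | 41 | 21.3 | 0.76 | 40 | 21.7 | 89.5% |

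The power column uses the noncentral t with 26 degrees of freedom and an SD at which the unadjusted t-test has exactly 80% power.

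Break-even is 1 − 1/1.038 = 3.7% for one covariate and 1 − 1/1.08 = 7.4% for two (about 8% by the power calculation). At R² = 0, two covariates cost about 3 points of power.

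**How well 30 women can fix an SD.** On 28 degrees of freedom, the 95% interval for an SD runs from 0.79 to 1.35 times the estimate. Around 24.4 that is roughly 19 to 33. Adjustment at R² = 20% multiplies the SD by √0.80 = 0.89, well inside that noise. In simulation with two covariates and a true R² of 20%, the estimated R² had a 95% range of 0.03 to 0.52.

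**Whether balloon time belongs in the model.** This depends on when counting starts. As an illustration, suppose that the interval is uniform over 0–3 h (SD 3/√12 = 0.866 h), that counting runs from randomization to 12 h of balloon time, and that 145 contractions are spread over 12 to 20 h (12.1 to 7.25 per hour). The interval then contributes an SD of 10.5 to 6.3 contractions, and (10.5/24.4)² to (6.3/24.4)² is about 18% to 7% of the variance. But Section 3.1 counts over the whole time the balloon is in place, and Sections 12.1 and 12.2 refer to labor. No section starts the count at randomization. Under the Section 3.1 window this link largely disappears.

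**The case against.** The strongest reply is that an unadjusted rank test is valid under randomization, that its error rate already allows for chance imbalance, and that a simple analysis suits a 30-woman pilot. All of that stands, and it is why the Mann-Whitney test should stay as planned.

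Three stronger readings are tempting, and the documents support none of them.

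- **That precision is certainly lost.** This needs an R² that appears nowhere. Both variables are truncated by eligibility (Bishop below 6, balloon below 3 h), which tends to weaken correlation, and at low R² adjustment does harm.
- **That the pilot SD will be too large for a future trial.** The Mann-Whitney test neither produces nor inflates an SD. An unadjusted SD is the right input for an unadjusted trial and a conservative one for an adjusted trial. The residual SD could also be computed later if the covariates are recorded.
- **That balloon time fixes drug exposure at 9 to 12 h and so drives the count.** Section 6.2 makes 12 h a maximum: balloons may be expelled early or removed after membrane rupture. The Section 3.1 count window also includes time before randomization.

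Two practical objections also stand. Criterion 11 needs only a check against 3 h, and Section 8 does not list the placement-to-randomization interval among the abstracted data. And Section 12.2 expects 25% intrapartum cesareans, so some women will have no time to complete dilation; ordinary regression of that time on Bishop score would mishandle them.

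The gap between a plan made only of tests and a pilot sized for estimation remains.

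**Conclusion.** The point holds as a modest, optional improvement. Section 12.3 does not commit to the estimates that the sample-size rationale calls for, and it leaves a baseline variable unused that is known for every woman.

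The benefit that does not depend on R² is a prespecified difference with its interval and an SD for planning. The precision benefit is conditional. A Bishop-only model needs an R² above about 4% to gain anything, and a two-covariate model about 7–8%. At an assumed 20%, the gain is equivalent to 36 or 35 women instead of 30. These figures assume a linear model and scale the plan's own 25-contraction difference, whose SD is undisclosed. Thirty women will estimate R² and the residual SD only roughly, so both should be presented as imprecise.

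**What to change.** In Section 12.3:

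1. Keep the Mann-Whitney test as planned.
2. Add a supporting regression of the contraction count on arm and pre-randomization Bishop score, naming the exam used. Report unadjusted and adjusted differences with 95% CIs, and the raw and residual SD. Rank ANCOVA is an alternative if a rank basis is preferred; the SDs would still come from the linear model.
3. Add balloon-to-randomization time as a second covariate only if the count is defined from randomization and placement time is made a recorded data item.
4. Use Bishop score as a covariate for the time outcomes only with a method that handles women delivered by cesarean before complete dilation, such as a time-to-event analysis that treats it as a competing event.

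The cost is a few lines of text and code, and one degree of freedom (two with balloon time) in a supporting analysis. The Bishop-only version should need no new measurement, provided the score is entered in the study database. The balloon covariate needs one extra recorded time.

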13. POTENTIAL CONTINGENCY PLANS

There may be slower than expected enrollment in the study, thus we plan to seek approval to advertise in all practices delivering at LPCH. We plan to recruit additional research staff support to assist in recruitment in the case of slower than expected enrollment.
